8.6.1 Missing Data

Missing data from subjects who withdraw from the study, including AEs and any follow-up, will be included in the primary endpoint analysis in the ITTI population. Assuming Missing at Random (MAR), multiple imputation will be the primary imputation method for handling the missing data. Sensitivity analysis using tipping point analysis under Missing Not at Random (MNAR) will be also accessed for the primary endpoint analysis in the ITTI population.

8.7 Interim Analyses

There is no interim analysis planned.

9.0 ETHICS

9.1 Institutional Review Board or Independent Ethics Committee

An Ethics Committee will approve the final protocol, including the final version of the ICF and any other written information and/or materials to be provided to the subjects. The Investigator will provide the Sponsor or CRO with documentation of IRB/IEC approval of the protocol and informed consent before the study may begin at the study site(s). The Investigator will submit the written approval to the Sponsor or representative before enrollment of any subject into the study.

The Sponsor or representative will approve any modifications to the ICF that are needed to meet local requirements.

The Investigator will supply documentation to the Sponsor or CRO of required IRB/IEC's annual renewal of the protocol and any approvals of revisions to the informed consent document or amendments to the protocol.

The Investigator will report promptly to the IRB/IEC any new information that may adversely affect the safety of subjects or the conduct of the study. Similarly, the Investigator will submit written summaries of the study status to the IRB/IEC annually, or more frequently if requested by the IRB/IEC. Upon completion of the study, the Investigator will provide the ethics committee with a brief report of the outcome of the study, if required.

The Sponsor or representative will provide Regulatory Authorities, Ethics Committees, and Investigators with safety updates/reports according to local requirements, including SUSARs, where relevant.

9.2 Ethical Conduct of the Study

This study will be conducted and the informed consent will be obtained according to the ethical principles stated in the Declaration of Helsinki (64th WMA General Assembly, Fortaleza, Brazil, October 2013)⁷, the applicable guidelines for GCP (CPMP/ICH/135/95), or the applicable drug and data protection laws and regulations of the countries where the study will be conducted.

Good Clinical Practice is an international ethical and scientific quality standard for designing, conducting, recording, and reporting studies that involve the participation of human subjects. The study will be conducted in compliance with GCP and the applicable national regulations so as to assure that the rights, safety, and well-being of the participating study subjects are protected consistent with the ethical principles that have their origin in the Declaration of Helsinki.

9.3 Subject Information and Informed Consent

The ICF will be used to explain the risks and benefits of study participation to the subject in simple terms before the subject will be entered into the study. The ICF contains a statement that the consent is freely given, that the subject is aware of the risks and benefits of entering the study, and that the subject is free to withdraw from the study at any time. Written consent must be given by the subject and/or legal representative, after the receipt of detailed information on the study.

The Investigator is responsible for ensuring that informed consent is obtained from each subject or legal representative and for obtaining the appropriate signatures and dates on the informed consent document prior to the performance of any protocol procedures and prior to the administration of study drug. The Investigator will provide each subject with a copy of the signed and dated consent form.

10.2 Data Handling and Record Keeping

It is the Investigator’s responsibility to maintain essential study documents (protocol and protocol amendments, completed eCRFs, signed ICFs, relevant correspondence, and all other supporting documentation). The study site will plan on retaining such documents for approximately 15 years after study completion. The study site will retain such documents until at least 2 years after the last approval of a marketing application in an ICH region and until there are no pending or contemplated marketing applications in an ICH region or at least 2 years after the formal discontinuation of clinical development of the investigational product. These documents will be retained for a longer period if required by the applicable regulatory requirements or the hospital, institution, or private practice in which the study is being conducted. Subject identification codes (subject names and corresponding study numbers) will be retained for this same period of time. These documents may be transferred to another responsible party, acceptable to the Sponsor, who agrees to abide by the retention policies. Written notification of transfer must be submitted to the Sponsor. The Investigator must contact the Sponsor prior to disposing of any study records.

For studies conducted outside the US under a US Investigational New Drug Application (IND), the Principal Investigator must comply with US FDA IND regulations and with those of the relevant national and local health authorities.

10.3 Direct Access to Source Data/Documents

The Investigator will prepare and maintain adequate and accurate source documents to record all observations and other pertinent data for each subject randomized into the study.

The Investigator will allow the Sponsor, the CRO, and authorized regulatory authorities to have direct access to all documents pertaining to the study, including individual subject medical records, as appropriate.

10.4 Investigator Information

10.4.1 Investigator Obligations

This study will be conducted in accordance with the ICH Harmonized Tripartite Guideline for GCP (GCP, 1996⁸); the US CFR Title 21 parts 50, 54, 56, and 312; and European Legislation; and the ethical principles that have their origin in the Declaration of Helsinki.

The Investigator agrees to conduct the study in compliance with this protocol after the approval of the protocol by the IEC/IRB in compliance with local regulatory requirements. The Investigator and the Sponsor will sign the protocol to confirm this agreement.

10.4.2 Protocol Signatures

After reading the protocol, each Investigator will sign the protocol signature page and send a copy of the signed page to the Sponsor or representative ([Appendix 1](#)). By signing the protocol, the Investigator confirms in writing that he/she has read, understands, and will strictly adhere to the study protocol and will conduct the study in accordance with ICH Tripartite Guidelines for Good Clinical Practice⁸ and applicable regulatory requirements. The study will not be able to start at any site where the Investigator has not signed the protocol.

10.4.3 Publication Policy

The data generated by this study are confidential information of the Sponsor. The Sponsor will make the results of the study publicly available.

Independent analysis and/or publication of these data by the Investigator or any member of his/her staff are not permitted without prior written consent of the Sponsor. Written permission to the Investigator will be contingent on the review by the Sponsor of the statistical analysis and manuscript and will provide for nondisclosure of the Sponsor's confidential or proprietary information. In all cases, the parties agree to submit all manuscripts or abstracts to all other parties 60 days prior to submission. This will enable all parties to protect proprietary information and to provide comments based on information that may not yet be available to

other parties. The publication policy with respect to the Investigator and study site will be set forth in details in the Clinical Trial Agreement.

10.5 Financing and Insurance

The Sponsor will obtain liability insurance, which covers this study as required by local law and/or national regulations and/or ICH guidelines, whichever is applicable. The terms of the insurance will be kept in the study files.

11.0 STUDY MANAGEMENT

11.1 Monitoring

11.1.1 Data Safety Monitoring Board

This study will be monitored by an independent DSMB consisting of a PK specialist, statistician, chairing physician, and an independent physician. Further details will be provided in a DSMB charter.

11.1.2 Monitoring of the Study

The Sponsor has engaged the services of a CRO to perform all monitoring functions within this study. Study monitors will work in accordance with the CRO's SOPs and have the same rights and responsibilities as monitors from the Sponsor organization. Monitors will establish and maintain regular contact between the Investigator and the Sponsor.

Monitors will evaluate the competence of each study site, informing the Sponsor about any problems relating to facilities, technical equipment, or medical staff. During the study, monitors will check that written informed consent has been obtained from all subjects correctly and that data are recorded correctly and completely. Monitors are also entitled to compare entries in eCRFs with corresponding source data and to inform the Investigator of any errors or omissions. Monitors will also control adherence to the protocol at the study site. They will arrange for the supply of investigational product and ensure appropriate storage conditions are maintained.

Monitoring visits will be conducted according to all applicable regulatory requirements and standards. Regular monitoring visits will be made to each site while subjects are enrolled in the study. The monitor will make written reports to the Sponsor on each occasion that contact with the Investigator is made, regardless of whether it is by phone or in person.

During monitoring visits, entries in the eCRFs will be compared with the original source documents (source data verification). For all entries, 100% of the data will be checked.

11.1.3 Inspection of Records

Investigators and institutions involved in the study will permit study-related monitoring, audits, IRB/IEC review, and regulatory inspections by providing direct access to all study records. In the event of an audit, the investigator agrees to allow the sponsor, representatives of the sponsor, or other regulatory agency access to all study records.

The principal investigator or sub-investigator should promptly notify the sponsor and its designee of any audits scheduled by any regulatory authorities and promptly forward copies of any audit reports or certificate received to the sponsor.

The investigator should promptly notify the sponsor and CRO of any audits scheduled by any regulatory authorities and promptly forward copies of any audit reports received to the sponsor.

11.2 Management of Protocol Amendments and Deviations

11.2.1 Modification of the Protocol

Any changes in this research activity, except those necessary to remove an apparent, immediate hazard to the subject, must be reviewed and approved by the sponsor or its designee. Amendments to the protocol must be submitted to the investigator's IRB/IEC for approval before subjects can be enrolled into an amended protocol.

11.2.2 Protocol Deviations

The investigator or designee must document and explain in the subject's source documentation any deviation from the approved protocol. The investigator may implement a deviation from, or a change of, the protocol to eliminate an immediate hazard to study subjects without prior IRB/IEC approval. As soon as possible after such an occurrence, the implemented deviation or change, the reasons for it, and any proposed protocol amendments should be submitted to the IRB/IEC for review and approval, to the sponsor for agreement, and to the regulatory authorities, if required.

A deviation from the protocol is an unintended or unanticipated departure from the procedures or processes approved by the sponsor and the IRB/IEC and agreed to by the investigator. A significant deviation occurs when there is nonadherence to the protocol by the subject or investigator that results in a significant, additional risk to the subject. Significant deviations can include nonadherence to inclusion or exclusion criteria, or nonadherence to regulatory regulations or ICH GCP guidelines, and will lead to the subject being withdrawn from the study.

Protocol deviations will be documented by the clinical monitor throughout the course of monitoring visits. Deviations from the protocol, including deviations of inclusion/exclusion criteria, will be assessed as "minor" or "major" in agreement with the sponsor. Deviations will be defined prior to unblinding. Principal investigators will be notified in writing by the

monitor of deviations. The IRB/IEC should be notified of all protocol deviations in a timely manner.

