and 10 PM, approximately]) and body temperature of subject will be also taken by site personnel at site at screening, Day 1 (prior to infusion), Day 2, Day 3, Day 5 and Day 8. Nasopharyngeal swab samples will be used for viral shedding based on quantitative polymerase chain reaction (qPCR) and cell culture. Those samples will be taken at screening, Day 2 (24 hours [± 4 hours] after the start of the study drug infusion), Day 3 (48 hours [± 4 hours] after the start of the study drug infusion), Day 5 (96 hours [± 4 hours] after the start of the study drug infusion), and Day 8 (168 hours [± 4 hours] after the start of the study drug infusion). Laboratory confirmation of influenza A infection will be defined as a positive result by qPCR or cell culture.

Safety Assessment:

For safety evaluations, subjects will be followed up from the time the ICF is signed until Day 110 (approximately 5 half-lives) after the administration of study drug. Safety assessments will occur throughout the study.

Adverse events (AE) or concomitant medications that are verified by the investigator will be recorded on the eCRF. Up to Day 8, any AE or concomitant medication will also be recorded by subjects on their diaries and the investigators will refer to the records for information. If there is any AE or concomitant medication after Day 8, subjects will be instructed to contact the Principal Investigator or sub-Investigator at any time.

If symptoms have not relieved up to Day 3, chest x-ray will be performed to determine presence of secondary complications of influenza A infection.

Subjects with suspicious ADE will be required to assess virus titer using the nasopharyngeal swab sample, Flu-iiQ™ and body temperature up to Day 8 after the day of ADE occurrence. If symptoms have not resolved or have worsened up to Day 8 after the day of ADE occurrence, same procedures will repeat.

Exploratory Assessment:

Blood sampling for PK analysis will be collected from the subjects on:

- Day 1 at pre-infusion (within 15 minutes prior to the beginning of the infusion), the end of infusion (+15 minutes), 1 hour (± 15 minutes) after the end of the infusion,
- Day 2 (24 hours [± 4 hours] after the start of the study drug infusion),
- Day 3 (48 hours [± 4 hours] after the start of the study drug infusion),
- Day 8 (168 hours [± 4 hours] after the start of the study drug infusion)
- Day 15 (± 2 days),
- Days 29, 57 and 110 (± 5 days) or at EOS visit

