4.3.3 Disease Diagnostic Criteria

The subjects will be screened for the presence of influenza A using a rapid influenza diagnostic test no more than 24 hours before treatment with study drug. The presence of influenza A will

be confirmed with qPCR or cell culture in only enrolled subject. Subjects who are positive for influenza A on the rapid influenza diagnostic test but negative on qPCR or cell culture will continue in the study and be followed up for safety purposes.

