5.4 Precautions and/or Overdose

There are no specific antidotes to CT-P27. Treatment of an overdose should be symptomatic.

Subjects who develop severe infusion-related reactions must have infusion terminated immediately, and the subject will be treated according to the best standards of care. These subjects will be followed up until stabilized, or until the reaction resolves.

During infusion of study drug, emergency drugs and equipment suitable for assistance during anaphylactic reactions will be available during infusion with study drug.

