5.7 Selection and Timing of Dose for Each Subject

All subjects will receive a single dose of study drug as randomized. As the study drug is administered at the study site, there are no specific instructions to be given to the subject as to how or when to take the study drug. It is critical that the infusion with study drug begins within 48 hours after the onset of influenza symptoms (window of +12 hours is allowed).

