8.4 Analysis Populations

8.4.1 Intent-to-Treat Population

The intent-to-treat (ITT) population is defined as all subjects randomized to study drug or placebo. All subjects will be included in the ITT as randomized even if they do not receive treatment. The secondary efficacy endpoint analysis and all baseline and demographic summaries will be performed on the ITT population.

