The primary efficacy endpoint will be analyzed using a Wilcoxon rank-sum test to assess differences between treatment groups (CT-P27 45 mg/kg vs placebo, CT-P27 90 mg/kg vs placebo), if every subject is followed until resolution of influenza symptoms and fever. The Wilcoxon rank-sum test will be used to test for a statistical significant difference of time to resolution between placebo and CT-P27. The results of the analysis will be summarized using p-values. The significant level will be set to 5%. If p-value is lower than 5%, it is considered that there is a significant difference between placebo and CT-P27. For subjects who withdrew from the study before the symptoms have resolved or if the symptoms did not resolve until the data cut-off, data will be censored at the latest date/time recorded on the diary or start date/time of study drug administration when there are no recorded data on the diary after study drug administration. If there is any censoring, the primary efficacy endpoint will be analyzed using Log-rank test and Gehans Wilcoxon test, and the result will be presented by p-values from the two tests. Also the table will present count of censoring reasons and 25th percentile, median, 75th percentile of time from administration of study drug to resolution. Kaplan-Meier plots will be presented.

CONFIDENTIAL

Statistical Analysis Plan

If there are no censoring data, sensitivity analysis using tipping point analysis under Missing Not at Random (MNAR) will be also performed to explain varying cases about average unobserved outcomes dropouts on two treatment groups.

Sensitivity Analyses which alter resolution conditions of primary efficacy analysis will be performed on the ITTI population. Following two endpoints will be assessed as described for the primary efficacy endpoint.

- Time (in days) to resolution of influenza symptom (respiratory and constitutional symptoms)

In the analysis, fever is not considered and the definition of resolution of symptom is the same as those of primary efficacy analysis.

- Time (in days) to resolution of influenza symptom and fever

In the analysis, threshold of resolution of fever is changed to 37.8°C and the definition of resolution of symptom is the same as those of primary efficacy analysis.

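### Protocol 11.2.2 requires withdrawal for significant deviations even after the single infusion, which removes no exposure and only cuts short outcome and safety data

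*Protocol*

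**What the plan says.** - **Protocol 11.2.2** defines a significant deviation as "nonadherence to the protocol by the subject or investigator that results in a significant, additional risk to the subject". It then names examples and their consequence: "nonadherence to inclusion or exclusion criteria, or nonadherence to regulatory regulations or ICH GCP guidelines, and will lead to the subject being withdrawn". This is withdrawal from the study. The wording is mandatory and does not separate dosed from undosed subjects. The next paragraph grades deviations as minor or major without linking either grade to the term significant.
- **Protocol 5.7:** "All subjects will receive a single dose of study drug as randomized". **Protocol 5.4:** "There are no specific antidotes to CT-P27".
- **Protocol 4.1** plans that "subjects will be followed up from the time the ICF is signed until Day 110 (approximately 5 half-lives) after the administration of study drug".
- **Protocol 4.3.4** encourages a subject who chooses to withdraw to return for the EOS assessments, asks for all reasonable attempts to obtain safety information, and rules out replacement. **Table 1, footnote 22** says more firmly that an EOS visit will be done after early termination.
- **SAP 10.1** censors at the last diary entry: "For subjects who withdrew from the study before the symptoms have resolved" is one of its two conditions, the other being non-resolution by the data cut-off. **Protocol 8.6.1** keeps withdrawals in the ITTI primary analysis by multiple imputation under missing at random.
- **SAP 5.1** excludes early-termination cases from the EOS summaries and only lists them.

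**The concern.** When treatment is ongoing, withdrawal can at least stop further exposure. Here the whole dose is given in one infusion, so a subject withdrawn after it has the same exposure as one who stays. What stops is the diary, the swabs and the scheduled safety visits, and it stops for the very subjects the protocol regards as carrying added risk.

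Two things are at stake. First, if the subject has not yet resolved, the primary outcome is cut off by a decision taken after randomisation. That decision may be related to how the subject is doing. Second, safety, ADE and immunogenicity data are thinned where they matter most; ADE incidence is named in the secondary objective.

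Discovery after dosing is plausible. Protocol 4.1 expects consent, screening, randomisation and treatment on the same day for most subjects. Section 11.1.2 has monitors check all entries later. Table 1, footnote 6 says screening laboratory results are not used for eligibility, while exclusions 7e and 7f are laboratory thresholds; those passages also need to be reconciled.

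**Working it through.** **1. What withdrawal after dosing changes.** Exposure: nothing, since there is one infusion and no specific antidote. Data: take a withdrawal on Day 3 purely as an illustration.

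- Swabs at Day 5 and Day 8 are lost.
- Diary Days 4 to 8 are lost: 5 of 8 days.
- Scheduled safety follow-up lost: 110 − 3 = 107 days.
- Both suspicious-ADE criteria in Protocol 6.2.5 concern the state at Day 8 or an illness after it, so scheduled observation ends before either can be assessed.
- The only post-dose immunogenicity sample is at Day 110 or EOS, so it is taken early or not at all.
- Adverse events are collected to Day 110/EOS (Table 1, footnote 21). SAEs reported spontaneously after an EOS visit are reported only if a causal link is suspected (6.2.1.6).

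**2. What happens to the primary outcome.**

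- Withdrawn after a documented 24-hour resolution: the event stands and nothing is censored.
- Withdrawn before resolution: censored under SAP 10.1; imputed under Protocol 8.6.1. SAP 10.3.1 applies multiple imputation to unanswered questionnaire items, and SAP section 13 does not declare a change for withdrawals.
- The tipping-point analysis is run only when nobody is censored (SAP 10.1 and 13), so it would not be available to examine this censoring.

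**3. Size of the power effect.** Inputs from Protocol 8.1: 63 per CT-P27 arm against 38 placebo, difference 1.8 days, SD 3 days, two-sided 5%, Wilcoxon rank-sum, 10% dropout.

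The plan's own figures come first. Enrolment: 164 / 0.90 = 182.2, rounded up to 183, as stated. Power by the normal approximation:

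z = 1.8 / (3 × √(1/38 + 1/63)) = 1.8 / 0.616 = 2.92; power = Φ(2.92 − 1.96) = 83.2%.

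Multiplying the sample sizes by the Wilcoxon efficiency 3/π = 0.955 gives z = 2.855 and power 81.4%. A simulated rank-sum test on normal data gives 81.1%. Both are close to the stated 80%. With the minimum efficiency of 0.864 the figure is 77.5%.

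Now assume a share w of evaluable subjects in each arm is withdrawn before resolution and contributes nothing. This is a worst case, because a censored subject still contributes time at risk. The documents give no value for w. Multiplying z by √(1 − w):

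| w | Power, efficiency 0.955 | Power, efficiency 0.864 |
|---|---|---|
| 0 | 81.4% | 77.5% |
| 2% | 80.7% | 76.7% |
| 5% | 79.5% | 75.4% |
| 10% | 77.3% | 73.1% |

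One subject is 1/38 = 2.6% of the planned placebo outcomes or 1/63 = 1.6% of a CT-P27 arm's. Withdrawals that fall within the planned 10% dropout cost no further power.

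**The case against.** Several stronger readings are tempting, and the documents do not support them.

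- **A reader might infer that every withdrawn subject's primary endpoint is censored.** SAP 10.1 censors only those who leave before resolution. The regular diary ends on Day 8, and a deviation found later may leave the outcome intact.
- **A reader might infer a breach of the ITT principle.** Protocol 8.4.1 says "All subjects will be included in the ITT as randomized even if they do not receive treatment", and ITTI adds only confirmed infection. A withdrawn subject stays in both sets. The problem is completeness of data, not membership.
- **A reader might see a contradiction with Protocol 4.3.3**, under which subjects not confirmed by qPCR or culture "will continue in the study and be followed up for safety purposes". Those subjects met inclusion criterion 6 through a positive rapid test and are not deviations. The section is a useful analogy and no more.
- **A reader might infer that safety follow-up is lost altogether.** It is reduced. Footnote 22 provides for an EOS visit, 4.3.4 asks for reasonable attempts to obtain safety information, and treatment-related events are followed to resolution or stabilisation (6.2.1.5). Events already recorded stay in the safety summaries.
- **A reader might argue that one such withdrawal changes the primary test.** That is so only if nobody else is censored. Other early withdrawals and subjects unresolved at cut-off have the same effect, so that weakness belongs to SAP 10.1.

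It is also fair to say that the trial is double-blind and that deviations are defined before unblinding, which limits deliberate arm-dependent decisions. Section 11.2.2 does not say when significance is judged. Blinding does not, however, prevent a decision related to the visible clinical course.

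What remains is a mandatory rule that, followed as written, ends scheduled observation of dosed subjects at added risk and gains nothing in exposure. Neither the EOS visit nor the reasonable-attempts wording restores the scheduled assessments.

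**Conclusion.** The point holds in a limited form. Section 11.2.2 states a rule that, for dosed subjects, yields less information than leaving them in the study, with no offsetting reduction in exposure. For those withdrawn before resolution, SAP 10.1 adds censoring that may be informative and that disagrees with Protocol 8.6.1. For all of them, the remaining scheduled follow-up to Day 110 is replaced by an early EOS visit that SAP 5.1 keeps out of the EOS summaries.

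The frequency is not stated, and the clause reaches only deviations carrying significant added risk, so the number may be small. The power effect is probably minor: under the worst-case assumption and efficiency 0.955, less than one percentage point at 2% withdrawn and about two at 5%, and nothing further if the dropout allowance absorbs them. The case rests on safety data and possible bias. It assumes that withdrawn from the study means the end of scheduled assessments, which is the plain reading and is consistent with 4.3.4 and footnote 22.

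**What to change.** Amend Protocol 11.2.2 so that a subject who has received any study drug and has a significant deviation, whether of eligibility or of GCP/regulatory requirements, remains in the already scheduled diary, swab and safety assessments to Day 110 unless consent is withdrawn. Record the deviation and review it at the blinded data review meeting. State how the term significant relates to the minor and major grades.

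Reconcile the amended text with 4.3.4 and Table 1, footnote 22 (encouraged or required EOS visit), and with Protocol 8.6.1 and SAP 10.1 (imputation or censoring of withdrawals). List any resulting change in SAP section 13.

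The cost is one paragraph in the protocol and short consistency edits elsewhere. No visit or procedure is added, because these subjects are already scheduled for them. The change concerns data collection only and proposes no dosing rule.
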